1.4.3 Risks Associated with Study Medications

The study medications, dapagliflozin and glimepiride, are very effective in glucose lowering. However, because of glucose lowering agents, they are also associated with hypoglycemia in general. However, because of the mechanism of action of dapagliflozin

(SGLT-2 inhibitor), the risk of hypoglycemic episodes is considered to be low. The recommended starting dose of dapagliflozin is 5 mg daily and glimepiride 1-2 mg daily. Therefore, we will start with low dose and titrate it up to optimal dose (dapagliflozin 10 mg daily and glimepiride 4 mg daily) based on participants' glucose monitoring and control to minimize hypoglycemic episodes. Symptoms attributed to hypoglycemia as well as glucose levels will be closely monitored in the trial.

Other potential risks of **dapagliflozin** are volume depletion, diabetes ketoacidosis, urinary tract and genital infection and hypotension. Subjects will be advised to maintain adequate fluid intake and monitor BP closely during study periods. If the study participant develops any of the mentioned risks, he/she will be managed and monitored according to standard care.

The common potential side effects of FDA approved **glimepiride** are hypersensitivity reaction and gastrointestinal reactions. All participants will be notified of risks of the study medications and are required to report to us as soon as they notice. The study personnel will report all directly observed adverse events and all adverse events spontaneously reported by the trial subject to University of Michigan IRB as adverse events (AE) and record those in CRF. All patients participating in this study will be treated in accordance to best standard of care per American Diabetes Association guidelines and recommendations.

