2.1 Primary objective

Evaluate the effects of 12-week treatment with dapagliflozin 5 mg daily escalating to 10 mg daily on measures of CAN as assessed by changes in HRV, changes in cardiovascular autonomic reflex tests (CARTs) and resting heart rate (RHR) compared with 12-week treatment with glimepiride 2 mg daily escalating the dose to 4 mg (no more than 4 mg daily) as needed based on glucose monitoring and control.

2.2 Secondary objectives:

Evaluate the effects of 12-week glycemic interventions on glucose control, BP, and weight.

2.3 Safety objective:

Evaluate the following parameters:

1. Incidence of symptomatic and asymptomatic hypoglycemia, glucose \leq 70 mg/dl, as defined by American Diabetes Association (ADA)
2. Incidence of severe hypoglycemia as defined by hypoglycemia requiring assistance from another person. It is also characterized by cognitive impairment that may be recognized or unrecognized and can progress to loss of consciousness, seizure, coma, or death, and it is reversed by administration of glucose.
3. UTIs
4. Any other AEs (see Section 1.4)

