- Description of AE.
- Date reported to IRB

It is important to distinguish between serious and severe AEs. Severity is a measure of intensity whereas seriousness is defined by the criteria in Section 6.4.2. An AE of severe intensity need not necessarily be considered serious. For example, nausea that persists for several hours may be considered severe nausea, but not a SAE. On the other hand, a stroke that results in only a limited degree of disability may be considered a mild stroke but would be a SAE.

Adverse Events based on signs and symptoms: When collecting AEs, the recording of diagnoses is preferred (when possible) to recording a list of signs and symptoms. However, if a diagnosis is known and there are other signs or symptoms that are not generally part of the diagnosis, the diagnosis and each sign or symptom will be recorded separately.

Adverse Events based on examinations and tests: Deterioration as compared to baseline in protocol-mandated glucose values and/or blood pressure values should therefore only be reported as AEs if they fulfil any of the SAE criteria or are the reason for discontinuation of treatment with the investigational product.

If deterioration in glucose concentration and/or blood pressure is associated with clinical signs and symptoms, the sign or symptom will be reported as an AE and the associated laboratory result/vital sign will be considered as additional information. Wherever possible the reporting investigator uses the clinical, rather than the laboratory term (e.g., anemia versus low hemoglobin value). In the absence of clinical signs or symptoms, clinically relevant deteriorations in non-mandated parameters should be reported as AE(s).

Any new or aggravated clinically relevant abnormal medical finding at a physical examination as compared with the baseline assessment will be reported as an AE.

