Staff Initials: _____

Subject ID: _____

CONCOMITANT MEDICATIONS WORKSHEET

Is the participant taken any concomitant medications at screening or during the prior 3 months					 No  Yes, Complete below		
Medication (Record Generic or trade name)	Reason for use (Medical History diagnosis or other reason, e.g. Prophylaxis)	Dose and units	Frequency	Route	Start Date (DD/MMM/YYYY)	Stop Date (DD//MMM /YYY)	Or tick if ongoing at Screening Visit
1.					___/___/___	___/___/___	
2.					___/___/___	___/___/___	
3.					___/___/___	___/___/___	
4.					___/___/___	___/___/___	
5.					___/___/___	___/___/___	
6.					___/___/___	___/___/___	
7.					___/___/___	___/___/___	
8.					___/___/___	___/___/___	
9.					___/___/___	___/___/___	
10.					___/___/___	___/___/___	

DATE / /
 mo day yr

SUBJECT ID STAFF INITIALS

Cardiovascular Autonomic Neuropathy Testing Worksheet

PREPAREDNESS FOR TESTING		
(If YES is answered to any of the questions below, patient is ineligible for CAN testing today. Reschedule the patient for testing another day and discard this form.)		
	No	Yes
1. Any food since in the past 12 hours?	(1)	(2)
2. Any liquids in the past 12 hours? (except water)	(1)	(2)
3. Any caffeine in the past 12 hours?	(1)	(2)
4. Any medication in the past 12 hours (excluding basal pump insulin)?	(1)	(2)
5. Any over-the-counter drugs in the past 12 hours (aspirin, antihistamines, nasal spray, etc.)	(1)	(2)
6. Any alcohol in the last 24 hours	(1)	(2)
7. Any tobacco in the past 12 hours?	(1)	(2)
8. Any vigorous exercise in the last 24 hours? (Any exercise not part of patient's daily routine, i.e., routine jogging O.K., but marathon running is not. NO exercise morning of test.)	(1)	(2)
9. Any emotional upset in the last 24 hours? (Depression, crying episodes, anxiety from personal trauma)	(1)	(2)
10. Acute illness in last 48 hours? (cold, flu, measles, etc.).	(1)	(2)
11. Any hypoglycemic episodes since midnight?	(1)	(2)
12 a) Fasting blood sugar value (finger stick method O.K.)	      mg/dl	
b) Below 50 or signs or symptoms of hypoglycemia?	(1)	(2)
VITAL SIGNS		

1. Height	_____. (cm)
2. Weight	_____. (kg)
3. BP	_____/_____ mmHg
4. Pulse	_____ BPM

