***** For research purposes only, cannot be used for billing and reimbursement *****

Technician's Signature: _____

Date: _____

Physician's Signature: _____

Date: _____

Adverse Event Monitoring

Subject ID: _____

Date: _____

Visit: _____

Was there any new or worsening adverse events reported?

- Yes, new event(s)
- Yes, worsening event(s)
- Yes, both
- No

Number of new or worsening adverse events: _____

Were any of the following events reported (check all that apply)?

- Urinary Tract Infection
- Genital Infection
- Hypotension
- Dehydration
- DKA
- Other

If other, describe:

*If there was a new or worsening adverse event, fill out a corresponding AE form for each event.

Completed By: _____ Date: _____

Adverse Event Form

Subject ID: _____

AE Number: AE __ __

Description of AE:

Date this Report Opened: _____

Date this Report Closed: _____

Most recently completed subject visit number (if event is reported in context of current visit, record today's visit number): _____

Date Adverse Event Started: _____
(can be approximate or unsure)

Date that the Study Staff Learned of the Event: _____

Date Adverse Event Abated: _____
(can be approximate or unsure, leave blank until abated)

Check if ongoing at conclusion of study

Indicate PI initial level of severity using the scale below:

- 1 - Mild AE - No treatment needed
- 2 - Moderate AE - Resolved with treatment
- 3 - Severe AE - Inability to carry on normal activities, required professional medical attention.
- 4 - Life-threatening or disabling AE
- 5 - Fatal AE

Indicate the final PI level of severity using the scale below:

- 1 - Mild AE - No treatment needed
- 2 - Moderate AE - Resolved with treatment
- 3 - Severe AE - Inability to carry on normal activities, required professional medical attention.
- 4 - Life-threatening or disabling AE
- 5 - Fatal AE

Indicate the PI initially relation to study participation.

Definite Probable Possible Unlikely Unrelated

Indicate the PI final relation to study participation.

Definite Probable Possible Unlikely Unrelated

Was the event expected? Yes No

What action was taken for the event reported (check all that apply)?

- No action taken
- Medication Prescribed
- Non-Drug Treatment Prescribed (e.g., physical therapy)
- Study Medication Dose Reduced
- Study Medication Stopped
- Outpatient Medical Visit
- Urgent Care Visit
- Emergency Room Visit
- Hospitalization
- Other

If other, describe: _____

Was medication stopped or reduced? Yes No

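### The adverse event checklist names only dapagliflozin's listed risks, no form shown records hypoglycaemia symptoms or assistance, and the CAN worksheet is thrown away when a session is rescheduled

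*Combined protocol and SAP*

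**What the plan says.** **Checklist.** The Adverse Event Monitoring form first asks whether any new or worsening event was reported and how many. It then asks "Were any of the following events reported (check all that apply" and offers urinary tract infection, genital infection, hypotension, dehydration, DKA and Other, the last followed by "If other, describe".

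**Named risks.** Section 1.4.3 says that dapagliflozin's other potential risks "are volume depletion, diabetes ketoacidosis, urinary tract and genital infection and hypotension", and that glimepiride's common side effects "are hypersensitivity reaction and gastrointestinal reactions". It links hypoglycaemia to both drugs, adding that with dapagliflozin "the risk of hypoglycemic episodes is considered to be low".

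**Hypoglycaemia.** Section 2.3 makes symptomatic and asymptomatic hypoglycaemia safety objective 1. Objective 2 is "Incidence of severe hypoglycemia as defined by hypoglycemia requiring assistance from another person". Section 5.2.2 has staff ask about its frequency and severity at each visit, and section 6.2 bases the assessment on symptoms, meter downloads and log sheets. Section 6.4.3 says that worsening glucose or blood pressure values "should therefore only be reported as AEs if they fulfil any of the SAE criteria" or lead to discontinuation. When such a change comes with symptoms, the sign or symptom is the reported event and the measured value is supporting information.

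**CAN worksheet.** If any readiness question is answered yes, the Cardiovascular Autonomic Neuropathy Testing Worksheet instructs: "Reschedule the patient for testing another day and discard this form". The protocol's list of appendices counts this worksheet among the case report forms, and section 6.1 makes the CRFs the source document.

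**The concern.** An event with its own box is more likely to be asked about, and is easier to count, than one that must be volunteered and written in. Here every named box belongs to one drug's risk list. If total adverse events, or one type of event against another, are compared between drugs, part of the difference could come from the form.

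The second issue is whether safety objectives 1 and 2 can be tabulated. They turn on symptoms and on help from another person. Staff must ask about severity, but an answer with no field to hold it may never become analysable data. Under section 12.4 the monitoring board reviews safety through AE and SAE reporting, so the gap would reach oversight as well as the final report.

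The third is record keeping. A discarded worksheet leaves no account of which HRV and reflex-test sessions were put off, or why, and those sessions produce the primary endpoint.

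**Working it through.** No formula applies. The check is a cross-match of forms against text, with a few counts.

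**1. Checklist against section 1.4.3**

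| Event in section 1.4.3 | Listed for | Named box on the form |
|---|---|---|
| Urinary tract infection | dapagliflozin | yes |
| Genital infection | dapagliflozin | yes |
| Hypotension | dapagliflozin | yes |
| Volume depletion | dapagliflozin | yes, as dehydration |
| Ketoacidosis | dapagliflozin | yes, as DKA |
| Hypersensitivity reaction | glimepiride | no |
| Gastrointestinal reactions | glimepiride | no |
| Hypoglycaemia | both | no |

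The count is 5 of 5 for dapagliflozin and 0 of 2 for glimepiride, with hypoglycaemia unprompted. Section 6.4.3 does not explain the pattern: it limits reporting of glucose and blood pressure values in the same way, yet hypotension has a box and hypoglycaemia has none.

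**2. Hypoglycaemia fields on the CRF pages shown**

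- Visit overviews, Visits 2 to 9 (8 of 8): an Assess Hypoglycemia tick with the name of the person who did it. No count, symptoms or assistance.
- Glucometer Download Data: no symptom or assistance field on the legible page.
- Personal Diabetes Record: blood sugar by time of day, pills taken and a comments column.
- Adverse Event Form: the severe grade rests on inability to carry on normal activities and professional medical attention, which differs from the assistance criterion in section 2.3.
- CAN worksheet: two yes/no questions, limited to the time since midnight and the moment of testing.

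Meter checks are asked for twice a day, in the morning and before dinner (section 6.4.8). The CGM covers two weeks of each 12-week period and records neither symptoms nor assistance.

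**3. Reach of the discard rule**

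- The worksheet has 12 yes/no readiness questions (items 1 to 11 and 12b), of which 2 (items 11 and 12b) concern hypoglycaemia. A yes to any of the 12 triggers the discard.
- Table 1 schedules HRV and CARTs at Visits 2, 5, 6 and 9: 45 participants × 4 = 180 planned sessions, all feeding the change in LF:HF ratio from baseline to week 12.
- Visit 2 precedes treatment and Visit 6 follows the wash-out, so on-treatment sessions are 45 × 2 = 90, one per participant per drug.
- For hypoglycaemia the rule therefore touches about one night per drug period. Visits 5 and 9 also include a meter download, so a low that was measured is kept.

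**The case against.** The best defence is that hypoglycaemia is closely followed by a route of its own: a query at every visit, meter downloads, log sheets and CGM. Its absence from the general checklist may simply reflect that. This stands as far as ascertainment goes. A reader might infer that hypoglycaemia is not collected; sections 5.2.2 and 6.2 show otherwise. What remains is narrower: the answers on symptoms and assistance have no visible field.

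A reader might also infer that the form tilts infection or volume-event counts against dapagliflozin. The documents do not support that. The same participants complete the same form in both periods, so for any one event type the wording is identical on both drugs. Only totals and comparisons across types are exposed, and section 12.2 plans no between-drug test of adverse events.

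It is also fair to say that staff fill in the form, that it opens with an unrestricted question, that Other is available, and that section 6.4.3 records every complaint, volunteered or elicited. If the list is never read aloud, the prompting effect is weaker. The documents do not say how it is used. Permission to record an event is still not the same as asking for it equally.

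Finally, a reader might take the discard rule to erase hypoglycaemia records mainly under glimepiride. Section 1.3 does expect more hypoglycaemia with a sulfonylurea, but the rule covers one night per period and measured lows survive on the meter. At most, an unmeasured overnight episode reported nowhere else would be lost. Section 6.4.3 also prefers diagnoses to symptoms in general, which softens its glucose rule without settling how a symptomatic low is named.

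**Conclusion.** The concern holds in a limited form, as a data-capture weakness that is cheap to repair.

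- **Checklist:** unequal elicitation by type of event (5 of 5 against 0 of 2, with hypoglycaemia unprompted). Total and cross-type comparisons can be skewed. The size cannot be given, because it depends on how staff use the form.
- **Hypoglycaemia:** on the forms shown, safety objectives 1 and 2 cannot be tabulated reliably, and section 6.4.3 can file a symptomatic low under its symptom. This assumes that no illegible or missing CRF page holds an episode field, which cannot be excluded.
- **CAN worksheet:** the discard instruction conflicts with section 6.1 and hides rescheduling at any of up to 180 primary-endpoint sessions. Its effect on hypoglycaemia data is small.

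None of this shows a bias for or against either drug on a given harm, and it does not touch the primary analysis model.

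**What to change.** 1. Add four boxes to the Adverse Event Monitoring checklist: hypersensitivity reaction, gastrointestinal reaction, symptomatic hypoglycaemia, and hypoglycaemia for which another person's help was needed. Ask the full list at every visit, whichever drug is being taken.
2. Record each hypoglycaemic episode with its glucose value, whether there were symptoms, and whether someone else had to assist, so that the entries match the definitions in section 2.3. If a page not shown already does this, refer to it in section 6.2 instead.
3. Replace the discard instruction on the CAN worksheet with: *keep this form, record the reason for rescheduling, and copy any hypoglycaemia to the hypoglycaemia/AE record.*
4. State in section 6.4.3 that a symptomatic or assisted low glucose is recorded as hypoglycaemia, and not only under its sign or symptom.

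The cost is a few boxes, a short episode record, one line on the worksheet and one sentence of protocol text, with slightly more data entry. Treatment, sample size and endpoints are unchanged.

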4.1 Inclusion criteria

1. Patients with type 2 diabetes as defined [34] on background metformin monotherapy who are not meeting ADA standard of care recommended glucose target [34]

2. Age ≥ 18 years

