4.2 Exclusion criteria

Subjects should not enter the study if any of the following exclusion criteria are fulfilled:

1. History of recurrent urinary tract infections
2. Patients with mycotic infections especially genital infection.
3. Severely hypotensive patients
4. History of unexplained microscopic or gross hematuria, or microscopic hematuria at visit 1, confirmed by a follow-up sample
5. Presence of hypersensitivity to dapagliflozin or other SGLT2 inhibitors (e.g. anaphylaxis, angioedema, exfoliative skin conditions)
6. Inability or refusal to comply with protocol
7. Current participation or participation in an experimental drug study in previous three months
8. Presence of history of diabetic ketoacidosis
9. Planned cardiac surgery or angioplasty within 3 months
10. Recent history of acute CV events such as MI, stroke, PAD within 3 months prior to enrollment
11. Patients with severe renal impairment or unstable or rapidly progressing renal disease or end stage renal disease.
12. Clinical conditions that could interfere with the cardiovascular autonomic function and heart rate variability (arrhythmias)
13. Severe hepatic insufficiency and/or significant abnormal liver function (defined as aspartate aminotransferase $>3\times$ upper limit of normal (ULN) and/or alanine aminotransferase $>3\times$ ULN) or creatinine kinase $>3\times$ ULN.
14. History of cancer other than basal cell carcinoma and or treatment for cancer within the last 5 years
15. Women of child-bearing potential who may be pregnant or lactating.
16. History of pancreas, kidney or liver transplant.

17. History of drug or alcohol abuse within 5 years
18. History of allergy to sulfa drugs
19. Presence of any condition that, in the opinion of the investigator would make it unlikely for the subject to complete the study.
20. Congestive heart failure (CHF) defined as New York Heart Association class III and IV

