5.6 Concomitant and post-study treatment(s)

The research staff will record all concomitant drugs used by the subject in the source documents. This is to include prescription, non-prescription, homeopathic medications and dietary/vitamin supplements. At the screening visit, medication use is to be carefully reviewed to ensure that no contraindicated medications as described in the protocol are being used (e.g., beta blocker agents, phentermine). At all subsequent visits, subjects will be asked to report any changes to their reported medication use and the source document updated accordingly. Queries regarding medication exclusions and contraindications are directed to the study principle investigator.

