3. **DO NOT TAKE ANY MEDICATIONS** for 12 hours prior to the test. This includes prescription and over the counter medications. Bring your medications (including your insulin) with you so that you can take them as soon as the testing is done. **IF YOU HAVE QUESTIONS ABOUT THIS, OR CONCERNS ABOUT SPECIFIC MEDICATIONS THAT YOU TAKE THAT ARE ON A VERY SPECIFIC SCHEDULE PLEASE CONTACT [name] PRIOR TO YOUR TEST.**
4. **NO ALCOHOL** for 24 hours before the test. Alcohol can interfere with the function of autonomic nerves, so any alcohol consumed in the 24 hours prior to your test may lead to invalid results.
5. **NO VIGOROUS EXERCISE** for 24 hours prior to the test **AND NO EXERCISE ON MORNING OF TEST.** Exercise that is part of your daily routine is fine in the 24 hours prior to testing (for example – routine jogging is okay, but running a marathon the day before testing is not – unless you run marathons on a daily basis).
6. **SIGNIFICANT EMOTIONAL UPSET** within 24 hours of testing can also lead to invalid test results. If something comes up the day before testing that is very upsetting, please call to discuss rescheduling the appointment.

7. ANY ACUTE ILLNESS IN THE 48 HOURS PRIOR TO TESTING (such as colds, flu's, dental work) may affect test results. If you are sick or feeling unwell, please call and we can discuss whether or not we should reschedule this test.

8. NO SMOKING FOR AT LEAST 12 HOURS PRIOR TO TESTING. If you do smoke, please do not have any cigarettes/cigars for at least the eight hours prior to testing.

Finally, please bring your blood glucose monitor with you. I will be asking you to check your blood sugar just before testing starts. Thank you and please call or email if you have any questions about the CAN testing or these instructions.

[name]: [contact]; [contact]

[name]: [contact]; [contact]

CASE REPORT FORM: SCREENING VISIT (VISIT 1)

SUBJECT ID: _____

VISIT DATE: _____

CONSENT SIGNED:

Eligibility Checklist: INCLUSION CRITERIA and EXCLUSION CRITERIA

Inclusion Criteria – All must be checked to be in study

- Type 2 diabetes
- At least 18 Years of age
- BMI \leq 45 kg/m²
- Background metformin monotherapy
- Willing and able to take an oral (by mouth) medication once per day for 2 periods
- WOMEN using an appropriate method of contraception during the course of the study (hormonal, IUD, or diaphragm).

EXCLUSION CRITERIA – If any are checked, cannot be in the study

- History of recurrent urinary tract infections

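### The Visit 1 eligibility checklist contradicts Section 4: it adds a BMI limit and omits the above-target glucose condition, planned cardiac surgery, lactation and creatine kinase.

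*Combined protocol and SAP*

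**What the plan says.** Section 4.1 has two inclusion criteria. One is age. The other is type 2 diabetes treated with metformin alone in patients "who are not meeting ADA standard of care recommended glucose target". Section 4.2 lists 20 exclusions. Item 9 is "Planned cardiac surgery or angioplasty within 3 months". Item 13 covers liver disease, transaminases, and "creatinine kinase" above three times the upper limit of normal (read here as creatine kinase). Item 15 is "Women of child-bearing potential who may be pregnant or lactating". Neither section mentions BMI.

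The Eligibility Checklist is part of the Screening Visit (Visit 1) case report form in the appendix. It has six inclusion items headed "All must be checked to be in study" and 16 exclusion items headed "If any are checked, cannot be in the study". The item on background treatment reads "Background metformin monotherapy" and stops there. Another inclusion item requires BMI of 45 kg/m² or below.

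**The concern.** The checklist headings are written as hard rules. Sections 6.1 and 9.2.1 make the case report form a source document, so the completed checklist is also the record that shows a patient was eligible. If it differs from Section 4, staff can complete it correctly and still enrol someone the protocol excludes, or refuse someone the protocol admits.

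The glucose condition matters most for the design. Every participant adds a glucose-lowering drug to metformin, and Section 1.4.3 acknowledges hypoglycemia as a risk of both study drugs. Sections 1.3 and 3.2 rest the comparison on similar glucose lowering in the two periods. Patients already at target are not the population for which that reasoning was written.

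**Working it through.** No figure in the plan needs to be reproduced. The check is an item-by-item comparison of Sections 4.1 and 4.2 with the checklist, followed by a search for any other control that covers each gap.

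| Subject | Section 4 | Checklist | Control elsewhere |
|---|---|---|---|
| BMI | No criterion | At most 45 kg/m², required | None; Sections 6.2 and 6.4.7 collect BMI but set no limit |
| Glucose above target | Required (4.1, criterion 1) | Absent | HbA1c is drawn at Visit 1, but no form item links it to eligibility |
| Planned cardiac surgery or angioplasty | Excluded (4.2, item 9) | Surgery and angioplasty appear only as events in the past three months | None found |
| Pregnancy | Excluded (item 15) | No exclusion item; a contraception item only | Urine test at Visit 1 (Table 1, Section 5.2.2), with the result recorded directly above the Eligible / Not Eligible box on the Visit 1 disposition form |
| Lactation | Excluded (item 15) | Absent | None specific |
| Creatine kinase | Excluded if above 3 × ULN (item 13) | Absent; general liver wording only | None: not in Table 1, Section 5.2.2 (Visit 1), 6.4.4 or 7.2 |

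**Count.** The 16 checklist exclusions correspond, in whole or in part, to 16 of the 20 in Section 4.2. Items 6, 9, 15 and 19 have no counterpart in the exclusion list (20 − 4 = 16). Item 6, on compliance, is partly covered by the inclusion item on willingness to take an oral medication. The pregnancy part of item 15 is covered by the urine test. That leaves item 9, item 19 (investigator's judgement) and the lactation part of item 15. Creatine kinase is a clause lost from within item 13, and the glucose target is half of an inclusion criterion.

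**Applying both lists to the same patient:**

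- On metformin alone and already at the glucose target: fails 4.1, passes the checklist.
- Angioplasty planned for next month and no recent event: fails 4.2, passes the checklist.
- BMI above 45 and otherwise suitable: passes Section 4, fails the checklist.
- Creatine kinase above the limit: fails 4.2, but no scheduled test would show it. Staff working from Section 4 alone would also miss this patient.

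**Smaller differences found in the same comparison.** The checklist has no numerical AST or ALT threshold and does not name unstable or end-stage renal disease. It adds sensitivity to glimepiride as an exclusion. It names three contraceptive methods and addresses women in general, whereas Section 5.1 asks for an acceptable method in women of child-bearing potential.

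**The case against.** The strongest reply is that the checklist is not the only gate. Section 5.2.2 applies the general entry criteria at preliminary screening, the physical examination worksheet asks about eligibility, and the final decision is recorded on a separate Visit 1 disposition form. Trained staff may well have Section 4 beside them. All of this is true and makes a wrong enrolment less likely. It does not remove the contradiction, because none of these other forms asks about the glucose target, a planned procedure or lactation. Nor does it help the patient with BMI above 45, whom the form refuses outright.

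A reader might infer that pregnancy is unguarded. It is not: the test is required and its result sits beside the eligibility decision. The gap is lactation.

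A reader might also point to beta-blockers, which Section 5.1 restricts because they affect the autonomic tests but which appear neither in Section 4.2 nor on the checklist. Section 5.6 requires medication to be reviewed for them at screening, and a concomitant medication worksheet is supplied. A checklist prompt would be tidier, but this is not an absent control.

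A further inference would be that a beta-blocker user, or anyone enrolled in error, must later be withdrawn without replacement, using one of 45 − 38 = 7 spare places. The documents do not support this:

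- Section 5.8, item 4, says that study medication can be discontinued, which is permissive and concerns the drug.
- Section 5.3 continues follow-up of all randomized participants, including those who stop medication.
- Section 12.1.1 defines the primary analysis set by non-missing endpoints in both periods, so an eligibility error does not by itself remove anyone.
- Section 12.3 already sets the margin against 10% non-completion (0.10 × 45 = 4.5 patients).

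Section 5.8.1 does end participation for a patient who fails to comply with the protocol, but nothing equates a site's enrolment error with that.

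**Conclusion.** The contradiction is real and should be corrected. The checklist carries one criterion with no basis in Section 4 (BMI) and lacks four elements that Section 4 requires: above-target glucose, planned cardiac surgery or angioplasty, lactation, and creatine kinase. The creatine kinase exclusion has a second fault within the protocol itself, since no scheduled test supports it.

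The size is a count of mismatched criteria, not of patients. The documents give no frequency for any of the affected groups, and no effect on power or on the primary estimate is shown. The conclusion assumes that staff apply the checklist as its headings direct and that the misspelled enzyme in item 13 is creatine kinase. The documents do not show whether Section 4 or the checklist reflects the sponsor's intention.

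**What to change.** 1. Reconcile the checklist and Sections 4.1 and 4.2 line by line so that both carry the same criteria, including the smaller differences listed above. The sponsor decides which version is intended for each, starting with BMI, the glucose target, planned cardiac procedures and lactation.
2. If the glucose condition stands, state which screening measurement decides it; Section 4.1 gives the target only by citation.
3. Reconcile the creatine kinase criterion with the laboratory schedule in Table 1 and Sections 5.2.2, 6.4.4 and 7.2, and correct the name of the enzyme.
4. Optionally, add a checklist prompt for the medications that Section 5.1 restricts and Section 5.6 has staff review at screening.

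The cost is an edit to one form and a short protocol clarification. Sample size and analysis are unaffected.
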